A prospective randomized clinical trial evaluating the effect of convective pre-warming on intra-operative thermoregulatory capabilities in patients enrolled in the TIGER anesthesia perioperative protocol

PI: [name], BS¹
Medical Student

Co-PI: [name], MD²
Professor

Co-I: [name], CRNA²

Co-I: [name], RN²

Co-I: [name], MPH²

¹University of Missouri School of Medicine

²Department of Anesthesiology and Perioperative Medicine

University of Missouri
[name]

NCT03876808

Contact: [name], BS

University of Missouri School of Medicine

[name]

[name]

[contact]

Email: [contact]

Summary

This prospective randomized clinical trial will assess the effect of pre-operative convective warming on intra-operative thermoregulation in patients undergoing gastrointestinal or genitourinary surgical procedures with the TIGER* anesthesia perioperative protocol.

*See addendum 1

Objectives:

Primary Endpoint:

1. Change in core temperature between induction of anesthesia and end of skin preparation (but before turning on the operating room forced-air warmer) as measured by a temperature-sensing Foley catheter

Secondary Endpoints:

1. Change in skin temperature between arrival to the holding area and departure to the operating room
2. Intraoperative temperatures
3. Skin temperature on arrival to the PACU (post-anesthesia care unit)
4. Differences in temperature changes between elderly (≥ 65 years) and younger patients

Clinical Hypotheses:

Primary Hypothesis:

We hypothesize that patients who are convectively warmed at 43°C for at least 60 minutes pre-operatively will have a higher core body temperature during the intraoperative period as measured by a temperature-sensing Foley catheter

Exploratory Hypothesis:

Patients who are convectively warmed prior to surgery will have

1. Temperatures that are significantly increased
 - a. At departure from the preoperative holding area

- b. In the OR after surgical preparation
 - c. On arrival to the PACU
2. Older (age \geq 65 years) patients will demonstrate a greater change in mean intraoperative temperature compared to younger patients

Background & Rationale:

By the year 2030 the geriatric presence in the United States, defined as any adult >65 years of age, is estimated to reach around 20% of the entire population.¹ Thus, understanding medical concepts as they relate to the elderly is becoming increasingly important. One such concept is that of hypothermia - a core body temperature $< 36^{\circ}\text{C}$ - for which age >65 has been found to be an independent risk factor.² This complication is especially prevalent intra-operatively due to use of general anesthetics, cool ambient operating room (OR) temperatures, and impaired thermal regulation in the elderly.³

The human body employs numerous mechanisms to maintain thermal homeostasis including: behavioral means of thermoregulation, sweating, pre-capillary vasodilation, non-shivering and shivering means of heat production, and arteriovenous shunt vasoconstriction.⁴ The first, and arguably most important, regulatory response to occur is that of vasoconstriction, which normally results in redistribution of blood from the relatively cool periphery to the warmer core compartment in order to confine metabolic heat to the central tissues.^{2,5} Patients undergoing general anesthesia experience reduced vasoconstriction due to decreased cold response thresholds while patients undergoing epidural anesthesia experience sympathetic blocks resulting in blunted vasoconstrictive responses.^{2,5} All patients experience the afore mentioned side effects of anesthetics, however it has been proven that the elderly are more susceptible to hypothermia due to lower vasoconstriction thresholds - determined by a temperature gradient of 4°C between the periphery and core.

First explored by *Kurz et al.*⁶ in 1993, it was found that use of nitrous oxide and isoflurane anesthesia lead to an approximately 1.2°C lower vasoconstriction threshold of 33.9 ± 0.6 in the elderly versus 35.1 ± 0.3 in the young ($p < .01$). This subject was again looked at in a 1997 study wherein the vasoconstriction threshold during nitrous oxide and sevoflurane was observed to be decreased by approximately 0.8°C in the elderly at 35.0 ± 0.8 versus 35.8 ± 0.3 in the young ($p < .01$).⁷ This is relevant because intraoperative hypothermia has long been known to lead to adverse outcomes such as increased incidence of myocardial ischemia, arrhythmias, coagulopathic states, and wound infections.⁴ In a 2014 retrospective cohort study by *Billeter et al.*² patients experiencing core temperatures $<35^\circ\text{C}$ had a four times increase in mortality with complication rates increasing two fold and incidence of stroke increasing six fold. To counter this thermoregulatory failure in patients, numerous methods of warming have been practiced over time to augment the normal body response.

One method used to decrease intraoperative hypothermia is warming patients before surgery via skin surface warmers. Numerous studies have found that even brief periods of pre-warming can improve intraoperative temperatures significantly for as long as 75-90 minutes after induction.^{8,9} In procedures lasting less than 90 minutes, *Horn et al.*¹⁰ found that as little as 10 minutes of pre-warming decreased incidence of intraoperative hypothermia from 69% to just 13% while *Torossian et al.*¹¹ decreased the incidence from 60% to 38% in his study using a self-warming blanket for 30 minutes pre-operatively. Studies have also shown that longer pre-warming of 45-60 minutes can prevent hypothermia for up to 2 hours after induction.¹²

[figure not shown]
While significant research has been performed on the effects of warming patients before they undergo surgical procedures, scant evidence demonstrates the effect of pre-warming in the elderly. In one article specifically looking at pre-warming in the elderly (mean age ~72-73) it was found that, after pre-warming for 20 minutes, there was no significant change in incidence of hypothermia but there

was a significant difference in severity of hypothermia when it did occur.¹³ This study focused only on men undergoing transurethral resection of the prostate however, and suffers from lack of generalizability. With the proportion of the geriatric population continuing to expand, and the potential adverse effects resulting from their increased susceptibility to intraoperative hypothermia, it is of the utmost importance to look into methods to counter this dilemma and expand the database on the topic.

Study Design:

This will be a prospective randomized clinical trial performed at a single academic hospital. Due to the nature of the trial, the anesthesiologists and subjects will not be blinded to their group assignment, but the postoperative assessments will be. All subjects will receive standardized pre-operative preparations, induction, and intraoperative infusions, as dictated by the TIGER anesthesia perioperative protocol.

In addition to these measures, one group will undergo convective warming during the preoperative preparations, completed for a minimum of 60 minutes prior to entering the operating room, while the other group will undergo standard of care, which includes providing each patient with a warming gown that is not turned on as well as blankets and sheets with more blankets provided on patient request.

Study Procedures:

- I. Patient population: 40 patients undergoing gastrointestinal or genitourinary surgeries, who are enrolled in the TIGER anesthesia perioperative protocol
- II. Inclusion criteria:
 - a. ASA I-IV
 - b. Other inclusion criteria as delineated in the TIGER anesthesia perioperative protocol
- III. Exclusion criteria:
 - a. Inability to obtain written informed consent
 - b. Inability to obtain Foley catheter temperature recordings
 - c. Family history of malignant hyperthermia
 - d. Preoperative temperature $> 38^{\circ} \text{ C}$
 - e. Other exclusion criteria as delineated in the TIGER anesthesia perioperative protocol
- IV. Randomization: On the day of surgery, patients will be randomized to one of two groups:
 1. Warming group: This group will undergo pre-warming at a temperature of 43° C or a minimum of 60 minutes beginning upon arrival to the pre-operative room continuing until they are taken to the operating room. This will be achieved with blankets as well as the use of a Bair Hugger® heating gown.
 2. Standard of care group: this group will receive the standard of care during the preoperative period, which includes providing the patient with blankets and sheets, as well as additional blankets upon request. They will also wear a Bair Hugger® heating gown, but it will not be used for preheating prior to surgery.

V. Randomization will be stratified for the type of surgery (gastrointestinal versus genitourinary) in an effort to reduce confounding.

VI. Blinding: Due to the nature of this study, the anesthesiologist, nursing staff, operating room staff, and the subject will know to which group the subject has been assigned.

VII. Anesthetic management as outlined in the enhanced recovery protocol.

VIII. Postoperative pain management as outlined in the enhanced recovery protocol.

IX. Perioperative assessments

- a. Duration of pre-warming prior to surgery
- b. Temperature change from arrival in the pre-operative holding area to leaving for the operating room as measured by a skin-temperature thermometer.
- c. Temperature change, as measured by a Foley catheter sensor inserted, after induction of anesthesia to the end of surgical skin preparation.
- d. Temperature as measured with a Foley catheter sensor throughout the operative procedure.
- e. Temperature change between leaving the operating room and arrival in the Post Anesthesia Care Unit (PACU).
- f. Duration of hospital stay, estimated blood loss, transfusion requirements, and postoperative complications

X. Sample size and statistical consideration:

- a. This is a pilot study and, if pre-warming is successful at preventing intraoperative hypothermia, data from this study will be used to develop larger studies. We plan to enroll 20 patients per group for a total sample size of 40 subjects to obtain pilot data.
- b. Data will be analyzed using chi-square and t-tests as appropriate with $p < 0.05$ considered significant.

Risks:

- I. No adverse effects are currently expected through participation in this study other than possible sweating and discomfort in patients in the pre-warming group heated for more than one hour.
 - a. Patients in the pre-warming group will be warned of the potential for sweating or discomfort due to warmth during informed consent at the pre-operative clinic visit. If they feel uncomfortable during the pre-warming process, staff will turn down the warmers from 43C to 38C; if symptoms persist staff will turn the warmers off.
 - b. If significant adverse events other than sweating or discomfort occur, the gown will be turned off, standard of care for the event provided, and the investigators will be notified
- II. All identifiable information will be kept in a secure location and will not be given to anyone unaffiliated with the University Hospital except as required by law.
 - a. Despite efforts to maintain confidentiality, a small risk associated with breach of confidentiality is still present
- III. There are no anticipated financial risks to patients.

Benefits:

Direct Benefit -

- In the pre-warming group, patient's may feel warmer pre- and post-operatively. Patients may also have higher temperatures throughout the day of surgery which may contribute to decreased incidence of hypothermia and its adverse effects.

Indirect Benefit -

- Patients may benefit from taking part in this research to the extent that they are contributing to medical knowledge. The information learned from this study may benefit other patients with risk of low body temperatures during surgery in the future.

Costs:

Patients will be required to pay for any treatment considered standard of care for the procedure under which they will be going. Bair Hugger® gowns are included in standard of care measures (each patient is provided with one pre-operatively whether or not they are used) and thus using them throughout the morning, prior to surgery, does not increase cost.

Ethical Considerations:

- I. Patient Expectations:
 - a. This study is not double-blinded and thus patients in the experimental arm may expect improved outcomes due to participation.
 - b. Expectations of improved outcomes will be managed in the pre-operative clinic setting during the informed consent process.
 - c. Patients will be explicitly told that this trial measures temperatures and only a few post-operative clinical outcomes, thus they may not experience a tangible benefit.
- II. Patient Comfort:
 - a. Increasing pre-operative temperatures with convective heating methods may compromise patient comfort and cause sweating to occur;¹⁴ this will be clearly explained to all patients agreeing to participate in the study during the informed consent process.
 - i. If patients in the experimental arm begin to feel uncomfortable, the staff will lower the temperature of the

heating gown from 43°C to 38°C; if discomfort persists at 38°C, staff can turn the heating gown off

- b. Patient comfort may be compromised by use of Foley catheter temperature sensors; this will be mitigated by insertion of catheters post-induction.
 - i. Inserting Foley catheters is routine care for all of the surgeries studied in this trial and thus should not be exposing patients to the potential of more harm than is inherent in the process of surgery

III. Confidentiality:

- a. Investigators will have access to patient information and records.
- b. All paper files will be de-identified
- c. All computerized information will be de-identified and kept in files on password-secured computers in the University of Missouri Department of Anesthesiology
- d. A code key with identifiable information will be kept in a separate secure location

IV. Informed Consent:

- a. Informed consent will be obtained from all participating patients in the pre-operative clinic setting.
- b. This study is excluding vulnerable patients comprising of prisoners, minors, and those with mental disability in order to maintain the integrity of the informed consent process.

V. Managing Adverse Events:

- a. No adverse effects are currently expected through participation in this study other than possible sweating and discomfort in patients heated more than one hour.¹⁴
- b. If any adverse events should arise due to pre-warming measures, they will be documented in the patient's chart, disclosed to the PI, and observed in study results.

- c. If any serious adverse events occur due to pre-warming measures, that interfere with or require discontinuation of said measures, patient's will be treated with the standard of care for the event and it will be disclosed to the PI immediately for review of safety.

VI. Retention of Records:

- a. Paper patient records will be retained in a locked cabinet for no more than 7 years after completion of the study.
- b. For retention of computerized patient records, within 1 year of completion of the study they will be printed and held in a locked cabinet for no more than 7 years after completion of the study.

VII. Gender Considerations:

- a. This intervention is expected to affect both male and female patients and is not currently intended for use in only one sex.

References:

1. Centers for Disease Control and Prevention. The State of Aging and Health in America 2013. Atlanta, GA: Centers for Disease Control and Prevention, US Dept of Health and Human Services; 2013.

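### The age objective rests on a two-group split at 65 with only chi-square and t-tests named; a pre-specified model with age in years and an arm-by-age term should be reported alongside the 65-year contrast.

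*Combined protocol and SAP*

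**What the plan says.** Under Objectives, secondary endpoint 4 reads "Differences in temperature changes between elderly (≥ 65 years) and younger patients". Under Exploratory Hypothesis, item 2 predicts that older (65 or over) "patients will demonstrate a greater change in mean intraoperative temperature compared to younger patients".

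The whole analysis plan is Study Procedures X.b: "Data will be analyzed using chi-square and t-tests as appropriate with $p < 0.05$ considered significant". It assigns no test to any endpoint and mentions no regression, covariate or interaction. X.a sets the size: "We plan to enroll 20 patients per group for a total sample size of 40 subjects to obtain pilot data". Study Procedures V fixes the only stratification factor: "Randomization will be stratified for the type of surgery (gastrointestinal versus genitourinary) in an effort to reduce confounding". The number of older patients is therefore left to chance, overall and in each arm.

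The Background gives a reason for the cut. It defines the geriatric population by this age and describes hypothermia as a complication "for which age >65 has been found to be an independent risk factor". It also names the shortage of evidence on pre-warming in the elderly as the gap to be filled.

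**The concern.** A split at 65 treats a 30-year-old and a 64-year-old as alike, and a 64-year-old and a 66-year-old as different. If temperature change varies smoothly with age, the split discards what age says within each group. The loss grows as the groups become less equal, and nothing in the design controls that balance.

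The tests named also leave the question itself unsettled. Endpoint 4 can be read as an age effect over all patients or as a difference in the benefit of warming by age. Exploratory hypothesis 2 falls under a stem about warmed patients, so it could even mean a comparison within that arm alone. A two-group t-test of older against younger patients answers the first reading without adjusting for arm. Separate t-tests within age groups do not answer the second, because comparing two p-values is not a test of interaction.

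The Background makes age central to the rationale, and the data are meant to inform larger studies. An inefficient or ambiguous age analysis weakens what this pilot can pass on.

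**Working it through.** **Inputs from the protocol.** Cut at 65 (Objectives, secondary endpoint 4); N = 20 + 20 = 40 (X.a); p < 0.05, taken here as two-sided because sidedness is not stated (X.b); stratification by surgery type only (V). There is no power calculation or loss figure to reproduce.

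**Inputs assumed.** The protocol gives no age distribution, no expected share aged 65 or over, no shape or size of age effect, and no SD. The only related figure is a national projection for 2030, which "is estimated to reach around 20% of the entire population". I take a share p of 20-50%.

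**Step 1: loss from the cut when the effect is linear.** The efficiency of the split relative to a linear term is the squared correlation between age and the indicator of being 65 or over. For normal age this is φ(z)² / [p(1 − p)], where z is the normal quantile at 1 − p.

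| Share 65 or over | φ(z) | Efficiency | Loss | Equivalent N (40 × efficiency) |
|---|---|---|---|---|
| 50% | 0.399 | 0.159 / 0.25 = 0.637 | 36% | 25.5 |
| 40% | 0.386 | 0.149 / 0.24 = 0.622 | 38% | 24.9 |
| 30% | 0.348 | 0.121 / 0.21 = 0.576 | 42% | 23.0 |
| 20% | 0.280 | 0.078 / 0.16 = 0.490 | 51% | 19.6 |

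**Step 2: sensitivity to the assumptions.** With uniform age the efficiency is 3p(1 − p), so the loss is 25% at p = 0.5 and 52% at p = 0.2. An illustrative two-peaked mix of young and old patients gives about 18%. Normal age with 10% older patients gives 66%.

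**Step 3: power at N = 40 by simulation, two-sided 0.05.** The age effect is set as a correlation of 0.42 between outcome and the true age term. The interaction is set as a difference between arms of 0.9 residual SD per SD of that term.

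| True shape | Share 65 or over | Age effect: linear term | Age effect: cut | Interaction: linear term | Interaction: cut |
|---|---|---|---|---|---|
| Linear | 50% | 78% | 58% | 73% | 55% |
| Linear | 20% | 79% | 46% | 74% | 41% |
| Step at 65 | 50% | 58% | 80% | 56% | 77% |
| Step at 65 | 20% | 46% | 78% | 43% | 71% |

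The advantage reverses with the shape, by a similar amount.

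**Step 4: shapes in between.** Take a logistic rise centred at 65, with an assumed age SD of 13 years and 20-50% older patients. If the rise from 10% to 90% takes about 29 years, the linear term keeps 85-93% of the information and the cut 73-78%. If it takes about 14 years, the linear term keeps 70-84% and the cut 85-87%.

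**Step 5: older patients per arm.** With 20-50% older patients, each arm of 20 expects 4 to 10. Treating the count in each arm as binomial(20, p), the chance of three or fewer is 0.411 at p = 0.2 and 0.107 at p = 0.3. The chance that this happens in at least one arm is 1 − (1 − 0.411)² = 65% and 1 − (1 − 0.107)² = 20%. A 65-year split of the warming effect could easily rest on very few patients.

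**The case against.** The strongest reply is that the loss figure belongs to an assumed shape. The protocol describes age by group throughout: a risk factor defined by a cut, and vasoconstriction thresholds in elderly and young patients (33.9 against 35.1, and 35.0 against 35.8). It gives no gradient. Under a step at 65, the linear term is the poorer analysis. This stands. The same material does not establish a step either, because two group means say nothing about the shape between them.

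Second, the cut is not arbitrary. Elderly against younger is the question the protocol asks, with a stated reason, so replacing it would change the endpoint. This also stands, and is why the 65-year contrast should remain a reported result.

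Third, linearity is a real assumption. A plot of 40 patients, or 20 per arm, checks it weakly, and a fitted effect at an older age leans on the line where patients are few. This too stands.

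Fourth, this is a secondary endpoint and an exploratory hypothesis in a pilot that claims no power for it. That limits the weight of the point. It does not remove it, since the pilot is meant to guide later work.

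A reader might infer that the split throws away 36-51% of the information as a matter of fact, and that continuous age restores it at no cost. The documents support neither. They fix none of the three assumptions behind the range, and the linear model carries a cost of its own. That endpoint 4 will be tested by a t-test is likewise an inference, since X.b says only that tests will be used as appropriate.

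**Conclusion.** The point holds in a conditional form. The plan defines its age objective by a cut at 65 and names no method that uses age in years, adjusts for arm, or estimates an arm-by-age term. A loss of 36-51% applies if age is roughly normal, its effect roughly linear, and 20-50% of patients are 65 or over; other age distributions tried gave 18% to 52%, and a 10% share gave 66%. With a step at 65, a linear term loses about as much as the cut would have lost under a linear effect. Neither analysis is safe alone.

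The gap that does not depend on shape is the missing arm-by-age estimate and the unsettled question of which age contrast is meant. This is a worthwhile, cheap improvement to a secondary and exploratory objective. It does not bear on the primary endpoint.

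**What to change.** In Study Procedures X.b, add for secondary endpoint 4 and exploratory hypothesis 2:

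- State whether the target is the effect of age on temperature change, the difference in the warming effect by age, or both.
- Pre-specify a linear model with arm, surgery type, age in years and arm-by-age. Report fitted effects with 95% CIs at selected ages including 65 (for example 50, 65 and 75), with a plot of outcome against age by arm.
- Report the 65-year contrast with its 95% CI alongside the model, as a result and not only as description, with the number of older patients in each arm.
- Say in advance that disagreement between the two will be read as uncertainty about the shape of the age effect, not settled by choosing the smaller p-value.

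The cost is a few lines of analysis text. Age is not in the list of perioperative assessments, but classifying patients at 65 already requires it, so no extra data collection is needed. The price is the linearity assumption, which is why both analyses should be shown.

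### The elderly endpoint and hypothesis compare old with young patients, not warmed with standard care, so as written they cannot show whether pre-warming works, or works differently, in the elderly

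*Combined protocol and SAP*

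**What the plan says.** Under Objectives, Secondary Endpoint 4 reads "Differences in temperature changes between elderly (≥ 65 years) and younger patients". Under Clinical Hypotheses, Exploratory Hypothesis 2 says that older "patients will demonstrate a greater change in mean intraoperative temperature compared to younger patients". In both, the named comparator is younger patients and no study arm is mentioned. Hypothesis 2 is listed below a lead-in about convectively warmed patients, but it is a complete sentence and does not follow from that lead-in grammatically.

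The Background & Rationale states the evidence gap: "scant evidence demonstrates the effect of pre-warming in the elderly". On hypothermia it also says that "age >65 has been found to be an independent risk factor", and it lists "impaired thermal regulation in the elderly" among the causes of intraoperative hypothermia.

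Study Procedures X.a gives the size: "We plan to enroll 20 patients per group", 40 in total, as a pilot. X.b is the whole of the analysis text: "Data will be analyzed using chi-square and t-tests as appropriate", with a 0.05 threshold. It is tied to no particular endpoint. Randomization is stratified by type of surgery only (Study Procedures V).

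**The concern.** The rationale asks what pre-warming does in the elderly. That is a comparison of warmed with standard-care patients aged 65 or over. If the question is whether the elderly respond differently, it is a comparison of that difference between age groups. The endpoint and the hypothesis instead compare age groups, which is not a randomised comparison and would exist without any intervention.

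The protocol's own background predicts an age difference. A significant result on Endpoint 4 could therefore be read as evidence about pre-warming when it shows only that older patients behave differently under anaesthesia. A null result could equally hide a real benefit in the elderly. These pilot data are meant to inform larger studies, so a misread age effect would carry forward.

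The wording also leaves open whether a greater change means a larger fall or a larger gain. The generic analysis text does not settle which contrast is intended.

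**Working it through.** **Inputs.** From the documents: 20 patients per arm, 40 in total; threshold 0.05; t-tests; stratification by surgery type. Assumed, because the documents do not give them: two-sided testing; 50%, 30% or 20% of patients aged 65 or over; these patients split equally between arms (10, 6 or 4 per arm); an age effect of 0.5 or 1.0 SD. There is no stated figure for this endpoint to reproduce.

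**1. What the written contrast measures.** Let the mean temperature change be *m* in young standard-care patients. Let *a* be the age effect under standard care, *w* the warming effect in the young, and *g* the interaction. The four cell means are *m*, *m+a*, *m+w* and *m+a+w+g*. Then:

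- Old minus young, all patients: *a + g/2*
- Old minus young, warmed arm only: *a + g*
- Warming effect in the elderly: *w + g*
- Difference in warming effect between age groups: *g*

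Neither old-minus-young contrast contains *w*, and neither separates *g* from *a*. Illustrative values in °C (assumed) show the consequence when all patients are used:

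| Scenario | *a* | *w* | *g* | Old − young, all (*a + g/2*) | Effect in elderly (*w + g*) |
|---|---|---|---|---|---|
| No warming effect | −0.4 | 0 | 0 | −0.4 | 0 |
| Equal benefit | −0.4 | 0.4 | 0 | −0.4 | +0.4 |
| Benefit in elderly only | −0.6 | 0 | 0.4 | −0.4 | +0.4 |
| Benefit in young only | −0.2 | 0.4 | −0.4 | −0.4 | 0 |

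With the warmed arm only, *a + g* is again −0.4 in all four scenarios if *a* is −0.4, −0.4, −0.8 and 0, with the same *w* and *g*. One observed value fits every answer to the question in the rationale.

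**2. How often the age contrast is significant when warming does nothing.** Power of a two-sided t-test (noncentral t), with noncentrality *d* / √(1/n_old + 1/n_young):

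| Comparison | Old v young (50% / 30% / 20%) | *d* = 0.5 SD | *d* = 1.0 SD |
|---|---|---|---|
| All patients | 20v20 / 12v28 / 8v32 | 34% / 29% / 23% | 87% / 81% / 69% |
| Warmed arm only | 10v10 / 6v14 / 4v16 | 19% / 16% / 14% | 56% / 49% / 40% |

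In simulations of the no-warming-effect case (20,000 trials per scenario), using a linear model with arm, age group, arm × age group and surgery type, the 95% interval for the interaction excluded zero in 4.8% to 5.2% of trials, as it should.

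**3. Precision of the contrasts that do answer the question.** The residual df are 40 − 5 = 35, with t₀.₉₇₅ = 2.03 and t₀.₈₀ = 0.85.

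- Interaction SE = √(2/n_old + 2/n_young) per arm. With 10/10, 6/14 and 4/16 this is 0.63, 0.69 and 0.79 SD.
- Interaction 95% half-width = 2.03 × SE: 1.28, 1.40 and 1.60 SD.
- Interaction detectable with 80% power = (2.03 + 0.85) × SE: 1.82, 1.99 and 2.28 SD.
- Arm difference in patients aged 65 or over: SE = √(2/n_old) = 0.45, 0.58 and 0.71 SD; 95% half-width 0.91, 1.17 and 1.44 SD.

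**The case against.** The strongest reply is that the protocol leaves the control arm unstated throughout. The primary hypothesis and the first exploratory hypothesis also predict higher temperatures without naming a comparator, and the two-group design supplies it. Read in that spirit, Hypothesis 2 may mean a greater warming response in older patients. The intention is plausible. But Hypothesis 2, unlike those items, does name a comparator, and it is younger patients. Applying the lead-in about warmed patients gives old versus young within one arm, still without a control.

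A second reply is that the permitted t-tests would allow warmed versus standard care within patients aged 65 or over. They would, but nothing commits the investigators to that test, and only the interaction needs a new model.

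Third, the significance rates above are correct detections of an assumed age effect, not false positives. That is right. They mislead only if an age difference is reported as a warming effect, and the documents do not say that it will be. The background also gives no size for an age effect on these endpoints. The rates illustrate the risk; the finding rests on the algebra.

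Fourth, the standard errors assume an equal split of elderly patients between arms, which stratification by surgery type does not secure. This stands. With 8 elderly patients among 40, ignoring surgery strata, a split of 2:6 or worse has a probability of about 24%. At 2:6 the interaction SE is √(1/2 + 1/6 + 1/18 + 1/14) = 0.89 SD.

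Finally, this is a secondary and exploratory matter in a pilot, and the right contrast can still be recovered from the data. That limits the severity but does not make the written contrast answer the stated question.

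**Conclusion.** The concern holds. Under either reading, Secondary Endpoint 4 and Exploratory Hypothesis 2 specify an old-versus-young contrast. That contrast carries no information on whether pre-warming works in the elderly and does not isolate whether it works differently in them. This conclusion follows from the wording and the cell-mean algebra and needs no assumed numbers. The significance rates depend on the assumed age effect and share of elderly patients, and the precision figures on that share and an equal split between arms.

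The correction should be made, but it is not critical: the items are secondary and exploratory, and the primary endpoint is untouched. Even correctly specified, the elderly question can only be estimated at this sample size, not tested.

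**What to change.** Restate Endpoint 4 and Hypothesis 2 as: the effect of pre-warming (warmed minus standard care) on temperature change differs between patients aged 65 or over and younger patients. State the expected direction and which temperature change is meant.

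In Study Procedures X.b, add a linear model with arm, age group, arm × age group and surgery type. Report the arm difference in each age group, since the difference in those aged 65 or over is closest to the stated evidence gap, together with the interaction. Give all three with 95% confidence intervals, labelled exploratory and not presented as significance tests. If the old-versus-young difference is also reported, label it as an age effect.

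The cost is rewording two items and adding one short model. Age, arm, surgery type and temperatures are already collected. The drawback is wide intervals: about ±1.3 to 1.6 SD for the interaction and ±0.9 to 1.4 SD for the arm difference in the elderly, and wider if the elderly split unevenly between arms.
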